6.2 Methods of minimising bias

6.2.1 Randomisation

We refer to the master protocol.

6.2.2 Blinding procedures

We refer to the master protocol.

6.2.3 Other methods of minimising bias

We refer to the master protocol.

6.3 Unblinding Procedures (Code break)

Not applicable.

7. STUDY POPULATION

This is a multi-centre study recruiting patients from 4 of the 7 study centres of the SHCS and 3 of the 6 study centres of the STCS (i.e. University Hospital Basel, University Hospital Zürich, and CHUV Lausanne). Both cohorts are representative for individuals living with HIV and solid organ transplants:

SHCS study centres:

- Department of Infectious Diseases, Bern University Hospital, University of Bern
- Division of Infectious Diseases & Hospital Epidemiology, University Hospital Basel
- Division of Infectious Diseases, University Hospital Lausanne, University of Lausanne
- Division of Infectious Diseases and Hospital Epidemiology, University Hospital Zurich, University of Zurich

STCS study centres:

- Klinik für Pneumologie, Universitätsspital Zürich
- Klinik für Nephrologie, Universitätsspital Zürich

- CHUV Lausanne, Service des maladies infectieuses
- CHUV Lausanne, Service de pneumologie
- CHUV Lausanne Service de néphrologie
- Universitätsspital Basel, Pneumologie
- Universitätsspital Basel, Transplantationsimmunologie & Nephrologie,

The cohorts are described in more detail elsewhere (8, 9, 16, 17). The study will be explained to eligible patients during their visit at the cohort centre. These visits will not be scheduled specifically for the purpose of this study.

7.1 Eligibility criteria

Inclusion and exclusion criteria as defined in the master protocol:

Inclusion criteria:

- All patients with either a chronic HIV infection or recipients of solid organs registered with informed consent from the SHCS and STCS cohorts aged ≥ 18 years
- Patients with solid organ transplantation of lungs or kidneys at least one month post-transplantation with a prednisone dose of 20mg or less.
- Additional consent for participation in the pilot trial
- Covid-19 vaccination recommended by treating physician

Exclusion criteria:

- Pregnancy
- Acute symptomatic SARS-CoV-2 infection, influenza or other acute respiratory tract infection
- Known allergy or contra-indications for vaccines or any vaccine components
- Any emergency condition requiring immediate hospitalization for any condition
- Patients with previous PCR documented SARS-CoV-2 infection and, or documented antibodies less than 3 months prior to randomisation
- Patients with solid organ transplantation (lung or kidney) with the following conditions:
 - Solid organ transplant recipients less than one month post-transplantation
 - Solid organ transplant recipients with the use of T-cell depleting agents in the last 3 months (i. e induction treatment in standard risk or high-risk immunological situation or rejection treatment).
 - Solid organ transplant recipients with the need of pulse corticosteroids (>100 mg prednisone or equivalent) in the last 1 month or rituximab in the last 6 months
 - Solid organ transplant recipients with the need of any kind of chemotherapy treatment

7.2 Recruitment and screening

We refer to the master protocol.

7.3 Assignment to study groups

We refer to the master protocol.

7.4 Criteria for withdrawal / discontinuation of participants

We refer to the master protocol.

8. STUDY INTERVENTION

8.1 Identity of Investigational Products (treatment / medical device)

(ICH/E6 6.2.1, 6.4.2, 6.4.4)

ICH: A description of the trial treatment(s) and the dosage and dosage regimen of the investigational product(s).

Describe all trial treatments for each arm of the study.

8.1.1 Experimental Intervention (treatment / medical device)

ICH: Name and description of the investigational product(s).

The COVID-19 mRNA Vaccine Moderna® is a white to off-white, sterile, preservative-free frozen suspension for intramuscular injection. The vaccine contains a synthetic messenger ribonucleic acid (mRNA) encoding the pre-fusion stabilized spike glycoprotein (S) of SARS-CoV-2 virus. The vaccine also contains the following ingredients: lipids (SM-102, 1,2-dimyristoyl-rac-glycerol-3-methoxypolyethylene glycol-2000 [PEG2000-DMG], cholesterol, and 1,2-distearoyl-sn-glycerol-3-phosphocholine [DSPC]), tromethamine, tromethamine hydrochloride, acetic acid, sodium acetate, and sucrose. The COVID-19 mRNA Vaccine Moderna® (100 µg) is administered intramuscularly as a series of two doses (0.5 mL each), given 28 days apart. The vaccine is injected in the deltoid muscle.

8.1.2 Control Intervention (standard/routine/comparator treatment / medical device)

ICH: Name and description of the investigational product(s).

The COVID-19 Vaccine, BNT162b2 (30 µg) commercial name Comirnaty® developed by Pfizer / BioNTech, is administered intramuscularly (IM) as a series of two 30 µg doses of the diluted vaccine solution (0.3 mL each) according to the following schedule: a single dose followed by a second dose 28 days later (12). BNT162b2 is supplied as a multiple-dose (5-dose) vial containing a frozen (between -80°C to -60°C suspension that is preservative-free. BNT162b2 must be thawed and diluted in its original vial with 1.8 mL of sterile 0.9% Sodium Chloride Injection, USP prior to administration. After dilution, the vial contains 5 doses of 0.3 mL per dose. After dilution, the multiple-dose vials must be stored between 2°C to 25°C and used within 6 hours from the time of dilution.

8.1.3 Packaging, Labelling and Supply (re-supply)

ICH: Also include a description of the dosage form, packaging, and labelling of the investigational product(s).

The COVID-19 mRNA Vaccine Moderna® is a suspension for Intramuscular Injection. 10 multiple-dose vials (each vial contains 10 doses of 0.5 mL). 5 mL dispersion in a vial (type 1 or type 1 equivalent glass) with a stopper (chlorobutyl rubber) and a flip-off plastic cap with seal (aluminium seal). Each vial contains 10 doses of 0.5 mL. Pack size: 10 multidose vials. Vials should be protected from light and be stored frozen between -25° to -15°C for a maximum of 30 days. The vaccine may not be stored on dry ice or temperature below -40°C. The vaccine should be prepared and administered by a trained healthcare professional using aseptic techniques to ensure sterility of the dispersion. The vaccine comes ready to use once thawed. One should not shake or dilute vials. Swirl the vial gently after thawing and before each withdrawal. COVID-19 mRNA Vaccine Moderna® vials are multidose. Ten (10) doses (of 0.5 mL each) can be withdrawn from each vial. All details are provided in the reference document (https://www.ema.europa.eu/en/documents/product-information/covid-19-vaccine-moderna-epar-product-information_en.pdf).

Comirnaty® (BNT162b2) is supplied as a multiple-dose (5-dose) vial containing a frozen (between -80°C to -60°C suspension that is preservative-free. BNT162b2 must be thawed and diluted in its original vial with 1.8 mL of sterile 0.9% Sodium Chloride Injection, USP prior to administration. After dilution, the vial contains 6 doses of 0.3 mL per dose. After dilution, the multiple-dose vials must be stored between 2°C to 25°C and used within 6 hours from the time of dilution. All details are provided in the reference document (https://www.ema.europa.eu/en/documents/product-information/comirnaty-epar-product-information_en.pdf).

8.1.4 Storage Conditions

The COVID-19 mRNA Vaccine Moderna® is provided as a frozen suspension [stored between -25° to -15°C] multi-dose vial containing 10 doses. The vaccine must be thawed prior to administration. After thawing, a maximum of 10 doses (0.5 mL each) can be withdrawn from each vial. Vials can be stored refrigerated between 2° to 8°C for up to 30 days prior to first use. Unopened vials may be stored between 8° to 25°C for up to 12 hours. After the first dose has been withdrawn, the vial should be held between 2° to 25°C and discarded after 6 hours.

Storage, defreezing and preparation of vaccine doses will be done according to the fact sheets provided by Moderna (<https://www.cdc.gov/vaccines/covid-19/info-by-product/moderna/downloads/storage-summary.pdf>).

Storage defreezing and preparation of vaccine doses will be done according to the fact sheets provided by Pfizer/ BioNTech (https://www.comirnatyeducation.ch/files/Checkliste_deutsch.pdf).

8.2 Administration of experimental and control interventions

8.2.1 Experimental Intervention

ICH: Description of and justification of the treatment(s) to be administered, including the name(s) of all the product(s), the dose(s), the dosing schedule(s), the route/mode(s) of administration, and the treatment period(s), including the follow-up period(s) for subjects for each investigational product treatment/trial treatment group/arm of the trial.

The **COVID-19 mRNA Vaccine Moderna®** (100 µg) is administered intramuscularly as a series of two doses (0.5 mL each), given 28 days apart (12). The vaccine is injected in the deltoid muscle <https://www.cdc.gov/vaccines/covid-19/info-by-product/moderna/downloads/prep-and-admin-summary.pdf>.

Preparation of vaccines (defreezing, dilution of ampules) and syringes for vaccination are done strictly according to the specifications of the producer and the guidelines by the BAG and eidgenössische Kommission für Impffragen (EKIF) https://www.bag.admin.ch/dam/bag/de/dokumente/mt/k-und-i/aktuelle-ausbrueche-pandemien/2019-nCoV/impfempfehlung-covid-19.pdf.download.pdf/Covid-19-Impfempfehlung%20f%C3%BCr%20mRNA-Impfstoffe_120121.pdf.

8.2.2 Control Intervention

ICH: Description of and justification of the treatment(s) to be administered, including the name(s) of all the product(s), the dose(s), the dosing schedule(s), the route/mode(s) of administration, and the treatment period(s), including the follow-up period(s) for subjects for each investigational product treatment/trial treatment group/arm of the trial.

The **Pfizer / BioNTech COVID-19 Vaccine, BNT162b2 (30 µg)**, is administered intramuscularly (IM) as a series of two 30 µg doses of the diluted vaccine solution (0.3 mL each) according to the following schedule: a single dose followed by a second dose 28 days later (12).

BNT162b2 is supplied as a multiple-dose (5-dose) vial containing a frozen (between -80°C to -60°C suspension that is preservative-free. BNT162b2 must be thawed and diluted in its original vial with 1.8 mL of sterile 0.9% Sodium Chloride Injection, USP prior to administration. After dilution, the vial contains 6 doses of 0.3 mL per dose. After dilution, the multiple-dose vials must be stored between 2°C to 25°C and used within 6 hours from the time of dilution. Details for storage and preparation are provided in the checklist by Pfizer / BioNTech (Checkliste für die Lagerung, Handhabung und Zubereitung des COMIRNATY® COVID-19 mRNA-Impfstoffs https://www.comirnatyeducation.ch/files/Checkliste_deutsch.pdf.

Preparation of vaccines (defreezing, dilution of ampules) and syringes for vaccination are done strictly according to the specifications of the producer and the guidelines by the BAG and eidgenössische Kommission für Impffragen (EKIF). https://www.bag.admin.ch/dam/bag/de/dokumente/mt/k-und-i/aktuelle-ausbrueche-pandemien/2019-nCoV/impfempfehlung-covid-19.pdf.download.pdf/Covid-19-Impfempfehlung%20f%C3%BCr%20mRNA-Impfstoffe_120121.pdf

8.3 Dose / Device modifications

(SPIRIT #11b)

Trial participants are vaccinated according to the producers' dosing recommendations. No adaptation of vaccine dosing is planned. In case of a serious adverse event following the application of a first dose, the second dose will not be given.

8.4 Compliance with study intervention

The application of the one-time injection by the treating physician (or a delegated person) will be documented in the trial platform data entry form and the batch number of the vaccine will be entered.

8.5 Data Collection and Follow-up for withdrawn participants

Patients have the right to withdraw the planned follow-up visits. Clinical outcomes for those patients will

be assessed from routinely collected cohort data.

8.6 Trial specific preventive measures

(ICH/E6 6.6.2; SPIRIT #11d)

ICH: Medication(s)/treatment(s) permitted (including rescue medication) and not permitted before and/or during the trial.

All patients included into the trial will continue all medication taken for the treatment of their chronic conditions. No drugs are prohibited that would exempt participation from the trial except use of ATG or rituximab within 6 months and pulse corticosteroids within 1 months prior to first vaccination for solid organ transplant patients. For transplanted patients with recent organ transplant receipt and / or more severe immune-suppressant treatment, decision to vaccinate patients and for trial participation is taken by the treating physicians by considering all benefit and potential harms for vaccination against Sars-CoV-2 in a particular patient.

Use of any drugs for the treatment of local or systemic adverse effects of vaccines is according to clinical judgement by clinicians.

8.7 Concomitant Interventions (treatments)

(ICH/E6 6.6.2; SPIRIT #11d)

ICH: Medication(s)/treatment(s) permitted (including rescue medication) and not permitted before and/or during the trial.

All concomitant drugs for patients included into the trial are recorded within the routine cohort based data collection structure (see master protocol). Physicians are free in the choice of any concomitant drugs for the treatment of HIV, immunosuppressants for transplanted patients or any other drugs used for the treatment of additional chronic conditions and take decisions for their use according to best clinical judgement and treatment guidelines. There are no particular drugs that are not permitted for their use during vaccination and follow-up.

Use of any drugs for the treatment of local or systemic adverse effects of vaccines is according to clinical judgement by clinicians.

8.8 Study Drug / Medical Device Accountability

(ICH/E6 6.4.7; SPIRIT 11c)

ICH: Accountability procedures for the investigational product(s), including the placebo(s) and comparator(s), if any.

Vaccines will be shipped to the pharmacies of the four participating university hospital in cooled containers guaranteeing temperatures during transport of -60 degrees C based on recommendations by the vaccine producers and the Bundesamt für Gesundheit. Vaccines will be shipped by cantonal vaccine storage facilities directly to hospitals for same day use or stored in refrigerators by university hospital pharmacies at the requested temperatures, defrozen and deluted according to prescribed rules of producers and prepared in sterile syringes for vaccination in batches of 6 and 5 vaccinations for the Pfizer / BioNTech and for the Moderna vaccine.

[figure not shown]
8.9 Return or Destruction of Study Drug / Medical Device

Does not apply. Since the vaccines will be a product which has received marked authorisation in Switzerland, unused vaccines will immediately be used for other patients vaccinated at the respective clinical sites based on the clinical judgement of physicians and according to the priority rules set by the BAG.

9. STUDY ASSESSMENTS

9.1 Study flow chart(s) / table of study procedures and assessments

Figure 1: Study flow chart.

9.2 Assessments of outcomes

9.2.1 Assessment of feasibility outcomes

We refer to the master protocol.

9.2.2 Assessment of immunological endpoints

We will assess pan-IgG anti S (RBD) (quantitative) and anti- N antibodies (qualitative) with the commercial Elecsys® Anti-SARS-CoV-2 tests at baseline and at 12 weeks following randomisation and vaccination (primary immunological endpoint).

We will assess SARS-CoV-2-binding antibody responses of the participants by analyzing the IgM, IgA and IgG responses to a wider range of SARS-CoV-2 proteins (S1, S2, RBD and N using an in-house method (ABCORA2.0) established at the Institute of Medical Virology (IMV), UZH (secondary immunological endpoint). The ABCORA 2.0 test allows for a parallel assessment of IgG, IgM and IgA reactivity to multiple antigens enabling a high-dimensional temporal resolution of antibody responses and a dissection between humoral responses to an infection and vaccination. We expect that the ABCORA2.0 antibody test will be more sensitive than the Elecsys® Anti-SARS-CoV-2 S antibody test.

Patients will be invited to see their treating physician 12 weeks after randomisation (see Study schedule). During baseline and follow-up visits this visit a blood sample will be taken (EDTA blood (2 x 7.5 ml)) and assessed for the above listed antibodies:

- 1ml for Elecsys® Anti-SARS-CoV-2 N and S tests (performed locally at each laboratory)
- 2ml EDTA Plasma for ABCORA 2.0 test (performed at IMV, UZH)

EDTA blood should be processed within 24h and EDTA plasma should be stored at -20°C. For ABCORA 2.1 antibody measurements plasma samples will be collected at each center and a collective shipment will be sent after baseline and at 12 weeks after randomisation and vaccination to the IMV, UZH. One sample will be stored according to SHCS and STCS protocols for later eventual analyses at the centers of University Hospital Zurich.

9.2.3 Assessment of clinical endpoints

Patients are informed to contact center physicians in case an asymptomatic or symptomatic SARS-Cov-2 infections was diagnosed outside the settings of participating cohort centers. Clinical endpoints will be assessed at 12 and 48 weeks, and during each cohort visits, that fall in between the trial specific visit dates.

- Newly PCR-confirmed asymptomatic Covid-19 infection (identified by the presence of anti-SARS-CoV-2 nucleocapsid antibodies, or PCR or rapid antigen test) and no related symptoms [(i.e. fever or chills, cough, shortness of breath or difficulty breathing, fatigue, muscle or body aches, headache, new loss of taste or smell, sore throat, congestion or runny nose nausea or vomiting, and diarrhea)] at any time during the 48 weeks of follow-up

During all visits at the trial centres (study specific at 12 and 48 weeks, as well as cohort visits) a PCR SARS-COV-2 test will only be conducted if the treating physician would also conduct such a test during clinical routine (e.g. exposure to infected individual). PCR tests done in between independently will be recorded with dates and results. In case of a positive test result, physicians will check for symptoms and patients will be followed-up according to clinical routine and physicians' judgement.

- Newly PCR-confirmed symptomatic Covid-19 infection with at least one of the following symptoms (i.e. fever or chills, cough, shortness of breath or difficulty breathing, fatigue, muscle or body aches, headache, new loss of taste or smell, sore throat, congestion or runny nose nausea or vomiting, and diarrhea) at any time during the 48 weeks of follow-up

During all visits at the trial centres (study specific at 12 and 48 weeks, as well as cohort visits) a PCR SARS-COV-2 test will only be conducted if the treating physician would also conduct such a test during clinical routine (e.g. COVID-19 related symptoms; exposure to infected individual). In case of a positive test result, physicians will check for symptoms and patients will be followed-up according to clinical routine and physicians' judgement.

- Severe COVID-19 infection with respiratory failure, evidence of shock (as diagnosed by a treating physician), clinically significant acute renal, hepatic, or neurologic dysfunction; admission to an intensive care unit; or death at any time during the 48 weeks of follow-up.
- COVID-19 burden of diseases (BOD), a composite of the above endpoints. The BID is will be scored as by using 0 for no COVID-19, 1 for non-severe COVID-19, and 2 for severe COVID-19.

The burden of diseases endpoint will be assessed by combining the before listed outcomes (i.e. no COVID-infection, non-severe COVID-19 infection

- Patient reported asymptomatic or symptomatic infections of household members.

Patients will be asked at the 12-week and 48-week visit if a household member was diagnosed with COVID-19.

9.2.4 Assessment of safety outcomes

9.2.4.1 Adverse events following vaccination

Any local symptom (redness or swelling or prolonged pain at injection side) continuation of normal daily activities during the first 7 days after vaccination

During the 12-week visit, patients will be asked if they had any local symptoms which limited their daily activities during the first 7 days after vaccination.

- Any systemic symptom (fever, generalized muscle or joint pain) limiting continuation of normal daily activities during the first 7 days after vaccination.

During the 12-week visit, patients will be asked if they had any systemic symptoms after randomisation which limited their daily activities during the first 7 days after vaccination.

- Any vaccine related symptom leading to contacting a physician during the first 7 days after vaccination

During the 12-week visit, patients will be asked if they had to contact a physician within 7 days after vaccination.

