10.1.3 Assessment of safety outcomes

10.1.3.1 Vaccine specific adverse events

Patients will be asked at the 4 week study visit about the following specific vaccine related adverse events:

- Any symptoms at injection site (redness, swelling or pain) limiting continuation of normal daily activities during the first 7 days following the booster vaccination?
- Any systemic symptoms (fever, muscle pain, joint pain) limiting continuation of normal daily activities during the first 7 days following the booster vaccination?
- Any vaccine related symptoms leading to physician contact during the first 7 days following the booster vaccination?

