To investigate the operability of a platform trial that is nested into two existing cohort studies and compare immune response, safety and clinical efficacy of the first two mRNA vaccines (Comirnaty® by Pfizer / BioNTech and COVID-19 mRNA Vaccine Moderna®, by Moderna) in immune compromised patients in the Swiss HIV and Swiss Transplant Cohort studies.

Feasibility endpoints:

We refer to the master protocol

Immunological endpoints (primary endpoint)

- Immune response (pan-Ig antibodies against the receptor binding domain (RBD) in the S1 subunit of the spike protein (pan-Ig anti-S1-RBD) of SARS-CoV-2.
- Newly PCR-confirmed asymptomatic SARS-CoV-2 infection

Clinical Endpoints

- Newly PCR-confirmed symptomatic SARS-CoV-2 infection
- Severe COVID-19 infection, hospitalization due to COVID-19 or death
- COVID-19 burden of diseases (BOD)
- Patient reported asymptomatic or symptomatic infections of household members.

Safety endpoints

- Adverse events from vaccines and
- Serious adverse events

Overall Design:

Multicenter randomised controlled, open-label, 2-arm sub-study pilot trial of a platform trial nested in two national cohorts

Number of Participants enrolled:

Eligible individuals are screened and flagged in both cohorts according to priority vaccination recommendations by the BAG. We will randomise 380 patients from both cohorts (recruitment of

patients from the Swiss Transplant Cohort Study will be limited to kidney and lung transplant recipients. These patients will be randomised to vaccination with Comirnaty® or the COVID-19 mRNA Vaccine Moderna®.

Intervention Groups and Duration:

Participants of the Swiss HIV Cohort and Swiss Transplant Cohort Studies with informed consent and no exclusion criteria will be centrally randomised via the trial platform to vaccination with mRNA vaccines COVID-19 mRNA Vaccine Moderna® or Comirnaty® (Pfizer / BioNTech) at day 0 with booster vaccines at day 21 and day 28, respectively. Antibodies against Sars-Cov-2 will be measured at baseline and 12 weeks with the Elecsys® anti-SARS_CoV_2 S and N (Roche Rotkreuz Switzerland) and ABCORA2.0 (IMV) assays. Vaccine related AE will be assessed at 12 weeks. SAE and asymptomatic or symptomatic Sars-Cov-2 infection (PCR confirmed) and hospitalisation, ICU admission, or death from any cause will be recorded at 48 weeks within the clinical trial platform and by routine cohort data collection.

STUDY SCHEDULE

	STUDY PERIOD					

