	Eligibility	Enrolment, randomisation & vaccination	Post-randomisation			
TIMEPOINT	Approximately -12 weeks	Day 0	Week 4	Week 12 (±7 days)	Week 48 (±7 days)	Continuous follow-up in the frame of the cohort
ENROLMENT:						
Eligibility screen ^a	X ^a					
Eligibility assessment	X					
Informed consent		X ^a				
Allocation		X ^b				
INTERVENTIONS:						
Intervention COVID-19mRNA Vaccine Moderna®		X	X			
Control Comirnaty® (Pfizer/BioNTech vaccine)		X	X			
ASSESSMENTS:						
BASELINE VARIABLES (will be exported from routine cohort data) Baseline blood sample	X					
IGG neutralizing antibodies post randomisation but prior to vaccination		X				
CLINICAL OUTCOMES:						
- Immune response IgG neutralizing antibodies	X ^e	X ^e		X ^c		
- Newly confirmed asymptomatic SARS-CoV-2 infection				X ^c	X ^{c,d}	X ^d
-Newly confirmed symptomatic SARS-CoV-2 infection				X ^c	X ^{c,d}	X ^d
- Severe COVID-19 infection with respiratory failure, evidence of shock, organ failure, admission to ICU, or death				X ^c	X ^{c,d}	X ^d
- Adverse events from vaccines				X ^c		
-Serious adverse events			X ^{c,d}	X ^c	X ^{c,d}	X ^d
- PCR confirmed symptomatic infections of household members				X ^c	X ^{c,d}	X ^d

^aContinuous assessment and selection from routinely collected cohort data

^bEnrolment and concealed allocation of patients with informed consent will be performed during the same visit when the study is explained to the patient, or, if preferred, during a separate arranged study visit.

^cAssessed in separate data entry form for the trial

^d Assessed by routine data collection from cohort data base

^eBaseline blood samples will be taken from previous cohort visits (no longer than 6 months) or during cohort and randomisation visits at day 0.

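### First sub-protocol: the three 7-day vaccine-reaction items are asked only at week 12, without naming the dose, although dose-1 answers could be taken at the week-4 dosing contact

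*Combined protocol and SAP*

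**What the plan says.** All of this concerns the first sub-protocol (Combined protocol and SAP) unless stated.

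- **Local symptoms**, section 9.2.4.1: "During the 12-week visit, patients will be asked if they had any local symptoms which limited their daily activities", with a 7-day window.
- **Systemic symptoms**, same section: "During the 12-week visit, patients will be asked if they had any systemic symptoms after randomisation which limited their daily activities", again within the 7-day window.
- **Physician contact**, same section: "During the 12-week visit, patients will be asked if they had to contact a physician within 7 days after vaccination".
- **Synopsis**: "Vaccine related AE will be assessed at 12 weeks".
- **Study schedule**: the row "Adverse events from vaccines" has one mark, at week 12. The row "Serious adverse events" is also marked at week 4, with footnotes for a separate trial form and for routine cohort data. Both vaccines are marked at day 0 and week 4.
- **Section 5.4.1** cites feasibility for limiting solicited collection to these three items. It gives no reason for the timing.
- **Section 6.1** describes the trial as open-label and lists safety among the planned comparisons.
- **Section 11.4.5** expects few safety issues and does not claim power to show a difference between arms.
- **Second-dose timing**: the synopsis gives day 21 in one arm and day 28 in the other. Sections 8.1.1 and 8.1.2 give 28 days in both.

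The third sub-protocol (Protocol, section 10.1.3.1) asks essentially the same three items earlier: "Patients will be asked at the 4 week study visit about the following specific vaccine related adverse events".

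**The concern.** The items concern a one-week period but are put to patients many weeks after it, although they attend in between. Longer recall tends to lose or misplace events, and misplacement matters more when there are two doses four weeks apart and the question does not say which is meant. Patients also know which product they received, so recall or willingness to report could differ by arm.

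At stake is the quality of the descriptive safety comparison, in a population for which the plan itself says safety data are missing (section 3.1). The plan's background (sections 3.3 and 3.4) shows why the dose matters: for the Moderna vaccine, systemic and severe reactions were more frequent after the second dose than after the first. An answer that cannot be tied to a dose cannot show whether that pattern holds here.

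**Working it through.** **1. The plan's own statistical figure.** The only one stated is the sample size (section 11.2: 90% response in both arms, 10-point margin, one-sided 0.025, 90% power):

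n per arm = (1.960 + 1.282)² × (0.9×0.1 + 0.9×0.1) / 0.10² = 189.13, rounded up to 190, so 380 in total.

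This agrees with the plan. The present point does not depend on it and would not change it.

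**2. Recall interval.** Recall interval = day of question − (dose day + 7).

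Inputs: dose 1 on day 0; dose 2 on day 28 (sections 8.1.1 and 8.1.2) or day 21 (one arm, synopsis); week 12 = day 84, with ±7 days giving days 77 to 91 (study schedule); week 4 = day 28.

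| Dose | Window closes | Asked at week 12 | Asked at week 4 |
|---|---|---|---|
| 1 (day 0) | day 7 | 84 − 7 = 77 days (70 to 84) | 28 − 7 = 21 days |
| 2 (day 28) | day 35 | 84 − 35 = 49 days (42 to 56) | window not yet closed |
| 2 (day 21) | day 28 | 84 − 28 = 56 days (49 to 63) | 28 − 28 = 0 days |

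A week-4 question shortens dose-1 recall by 77 − 21 = 56 days. It does nothing for a second dose given on day 28.

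**3. Effect of the conflict on second-dose timing.** If the synopsis were followed, dose-2 recall at week 12 would differ between arms by 56 − 49 = 7 days. If dose 1 were asked about at the second-dose contact, its recall would be 21 − 7 = 14 days in one arm and 21 in the other.

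**4. What recall error could do.** The documents give no recall rates, so these are assumed values for illustration only.

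- *Equal recall of 70% in both arms:* a true difference of 10 points is observed as 0.7 × 10 = 7 points.
- *Unequal recall, 90% against 70%, with the same true rate in both arms:* apparent difference = true rate × (0.9 − 0.7). The 95% half-width is 1.96 × √[p₁(1−p₁)/190 + p₂(1−p₂)/190].

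| True rate | Observed rates | Apparent difference | 95% half-width |
|---|---|---|---|
| 10% | 9% v 7% | 2 points | 5.5 points |
| 20% | 18% v 14% | 4 points | 7.4 points |
| 40% | 36% v 28% | 8 points | 9.3 points |

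Even this marked imbalance gives a spurious difference smaller than the half-width of the interval at 190 per arm.

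**5. Is the delay avoidable?** The schedule has a week-4 contact in both arms and a trial form for serious events at that point. Section 8.3 makes the second dose depend on whether a serious event followed the first, so some account of the interval after dose 1 is needed by then.

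**The case against.** The case on the other side has substance.

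- **Pooling of doses.** A reader might infer that both doses are merged into one answer and that reporting by dose is impossible. The text does not establish that. It refers only to vaccination, the case report form is not among the documents, and sections 9.3.3 and 10.1.2 refer the week-12 procedures and adverse-event follow-up to the master protocol, which is also not available. What stands is that the written wording is ambiguous.
- **Minor events.** A reader might infer that mild reactions will be under-reported. They are outside the endpoint: section 5.4.1 counts only symptoms that limit daily activities or lead to physician contact. Events of that kind are probably easier to remember, which weakens the recall argument without removing it.
- **Biased comparison.** A reader might infer that the open-label comparison is biased. Both arms get the same questions at the same visit, and nothing in the documents shows that recall differs by arm. It is possible, not shown.
- **The week-4 contact.** Section 9.2.3 names only weeks 12 and 48 as study-specific visits, the week-4 mark allows routine cohort data as well as the trial form, and section 8.4 describes the recorded injection as a single one. No patient interview at week 4 is described. That the items can be added there without an extra visit is a reasonable inference from the schedule, not a stated fact.
- **The third sub-protocol as precedent.** It covers one vaccination and asks at a scheduled follow-up visit. It shows that the questions work at 4 weeks on this platform, not that a dosing contact was the expected place for them.
- **The remedy.** It leaves the dose with the higher reported reactogenicity at 49 days and makes recall differ between doses. This stands and belongs in the fix as a caveat.

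**Conclusion.** The point holds as a modest improvement to safety data collection. Section 9.2.4.1, the synopsis and the schedule agree on week 12 as the only time for the three items. The feasibility reason covers how many items are asked, not when. Asking about dose 1 at week 4 would cut its recall interval from about 77 to 21 days, and naming the dose would make each answer attributable.

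This assumes that patients are seen at week 4 as the schedule shows, that second doses fall on day 28, and that the unseen master protocol and case report form do not already collect these items earlier or by dose.

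The documents do not support saying that the arm comparison is biased, or by how much. Equal under-recall would lower both rates and shrink a true difference; a spurious difference needs recall or reporting to differ by arm. No safety power is claimed, serious events are captured separately from week 4, and the primary immunological endpoint is untouched. The point is desirable rather than essential.

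**What to change.** 1. Add the three items to the week-4 trial form, asked about dose 1.
2. Word the week-12 items to refer to dose 2.
3. Compare arms within each dose. State that dose-1 and dose-2 rates were collected at different recall intervals (21 and 49 days) and should not be compared with each other without that caveat.
4. Reconcile the second-dose timing in the synopsis with sections 8.1.1 and 8.1.2, because it also sets the dose-2 recall interval and whether that interval is equal across arms.

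The cost is three questions on a form that the schedule already implies, about a minute of staff time at the dosing contact. No extra visit is needed and the sample size stays at 380. Dose-2 recall is not improved; that would need a contact or diary soon after its 7-day window, at greater cost.

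The third sub-protocol (Protocol, section 7.1) reports this sub-study as already conducted. For data already collected, the remaining step is to report the recall interval and state which dose the answers refer to, or that this is unknown.
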